#### **5.4. Pharmacokinetic (PK) Analysis Set**

The following PK Analysis Sets will be determined for each cohort separately.

##### **Concentration Analysis Set**

*The PK concentration population is defined as all subjects randomized and treated who have at least 1 concentration during the study.*

##### **Parameter Analysis Set**

*The PK parameter analysis population is defined as all subjects randomized and treated who have at least 1 of the PK parameters of primary interest during the study.*

#### **5.5. Treatment Misallocations**

Subjects who are randomized but never treated will not be included in either safety or efficacy analyses. For a randomized subject who took the incorrect treatment, he/she will be reported under the randomized treatment group for all efficacy analyses, but will be reported under the treatment they actually received for all safety analyses.

#### **5.6. Protocol Deviations**

##### **5.6.1. Deviations assessed prior to randomization**

See [Section 5.2.1](#)

##### **5.6.2. Deviations assessed post-randomization**

See [Section 5.2.2](#)

### **6. ENDPOINTS AND COVARIATES**

#### **6.1. Efficacy Endpoint(s)**

##### **6.1.1. Primary Endpoint**

- Maximum cystometric bladder capacity defined as maximal tolerable cystometric capacity or until voiding/leaking begins or at 40 cm H2O.

### 6.1.2. Secondary Endpoints

- Detrusor pressure at maximum bladder capacity;
- Presence of involuntary detrusor contractions (IDC);
- Bladder volume at first IDC;
- Bladder compliance.

Defined as  $\Delta\text{volume}/\Delta\text{pressure}$  during that change in bladder volume.

- Mean number of micturitions per 24 hours.

The mean number of micturitions per 24 hours will be calculated as the total number of micturitions divided by the total number of diary days collected at that assessment. This endpoint will only be calculated for subjects with >0 episodes at baseline.

- Mean number of catheterizations per 24 hours.

The mean number of catheterizations per 24 hours will be calculated as the total number of catheterizations divided by the total number of diary days collected at that assessment.\* This endpoint will only be calculated for subjects with >0 episodes at baseline.

\*Note: The number of diary days collected at that assessment is the number of calendar days that the diary has been completed on (even if this may not be a full 24 hour period). For example, if a diary has been completed for 3 complete days and the morning of the fourth day, this would count as 4 days. This derivation is the same for all the diary endpoints listed 'per 24 hours'.

- Mean number of micturitions and catheterizations combined per 24 hours.

The mean number of micturitions and catheterizations combined per 24 hours will be calculated as the total number of micturitions and catheterizations combined divided by the total number of diary days collected at that assessment.

- Mean number of incontinence episodes per 24 hours.

The mean number of incontinence episodes per 24 hours will be calculated as the total number of incontinence episodes divided by the total number of diary days collected at that assessment. This endpoint will only be calculated for subjects with >0 episodes at baseline.

- Mean urgency episodes per 24 hours if applicable (only for sensate subjects, ie, able to physically experience the sensation of urgency - as indicated in CRF).

The mean number of urgency episodes per 24 hours will be calculated as the total number of urgency episodes divided by the total number of diary days collected at that assessment. Urgency episodes are defined as Urgency marked as 'yes' in the diary. This endpoint will only be calculated for subjects with >0 episodes at baseline.

- Mean volume voided per micturition.

The mean voided volume per micturition will be calculated as sum of voided volume divided by the total number of micturition episodes with a recorded voided volume greater than 0, regardless of the number of available diary days at that assessment.

Note: missing or zero voided volume will not be included in this calculation

- Mean volume per catheterization.

The mean volume per catheterization will be calculated as sum of voided volume divided by the total number of catheterization volume greater than 0, regardless of the number of available diary days at that assessment. Note: missing or zero voided volume will not be included in this calculation

- Mean volume voided per micturition or catheterization.

The mean voided volume per micturition or catheterization will be calculated as sum of voided volume divided by the total number of micturition episodes with a recorded voided volume greater than 0, regardless of the number of available diary days at that assessment. Note: missing or zero voided volume will not be included in this calculation

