### **2.2.2. Secondary Endpoints**

#### **2.2.2.1. Efficacy Endpoints**

- Detrusor pressure at maximum bladder capacity.
- Presence of involuntary detrusor contractions (IDC).
- Bladder volume at first IDC.
- Bladder compliance.
- Mean number of micturitions and/or catheterizations/24 hrs.
- Mean number of incontinence episodes/24 hrs.
- Mean urgency episodes/24 hrs if applicable (only for sensate subjects).
- Mean volume voided per micturition or mean volume per catheterization.

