#### 4.1. Inclusion Criteria

Subject eligibility should be reviewed and documented by an appropriately qualified member of the investigator's study team before subjects are included in the study.

Subjects must meet all of the following inclusion criteria to be eligible for enrollment into the study:

1. Male or female subjects aged 6-17 years 11 months (age at time of first dose); that is subjects who have passed their sixth birthday but not reached their eighteenth birthday.
2. Subjects with stable neurological disease and clinically- or urodynamically-demonstrated NDO, confirmed urodynamically at Visit 2, by detrusor overactivity or decreased bladder compliance, with decreased maximum cystometric bladder capacity.

NOTE: Subjects with hypocontractile bladder, detrusor underactivity, or a 'flaccid' bladder should not be included.

3. Evidence of a personally signed and dated informed consent document indicating that the subject (or a legal representative) has been informed of all pertinent aspects of the study. In addition, an assent from the subject will be obtained when appropriate, and when the potential subject is capable of providing assent.
4. Female subjects who are of child-bearing potential (defined as  $\geq 9$  years old or have experienced menarche, whichever is earlier) must not be intending to become pregnant, currently pregnant, or lactating. The following conditions apply:
  - a. Subjects of childbearing potential must have a confirmed negative pregnancy test prior to randomization.
  - b. Subjects of child-bearing potential must agree to use effective contraception during the period of the trial and for at least 28 days after completion of treatment. Effective contraception includes abstinence.
  - c. Sexually active male subjects must agree to use effective contraception during the period of the trial and for at least 28 days after completion of treatment.

Further details of the definition of child-bearing potential and effective contraception may be found in Section 4.4.

5. Swallowing:
  - a. Subjects  $>25$  kg must already have the ability to swallow tablets whole, without chewing or crushing. The first dose of medication will be given in clinic under observation, and any subject not able to swallow tablets will be excluded from the study.

- b. Subjects  $\leq 25$  kg can either swallow the capsules whole or sprinkle on food.

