### **7.1.2. Bladder Diary**

A bladder diary will be completed for 3 consecutive days (with a minimum of 2 days) during the week prior to Visit 2 (baseline) and Visit 5 (Week 12), using an electronic capture device. The bladder diary may be completed over a weekend, if this is more convenient for the subject. Completion of the bladder diary prior to Visit 2 (baseline) should be begun only after previous treatment with prohibited concomitant medications has undergone a minimum washout appropriate to the drug so any clinical effect is at a minimum eg, 3 day minimum washout for oxybutynin, 7 day minimum washout for darifenacin and solifenacin. Daily micturition or catheterization frequency, volume of urine from each micturition or catheterization (for one of the days), incontinence episodes and urgency episodes (if appropriate) will be recorded. Urinary urgency is defined according to the [International Children's Continence Society](#) standards as the sudden and unexpected experience of an immediate need to void (Neveus, et al, 2006).

A proxy (eg, parent or teacher) may assist with completion of the diary if necessary. Contact should be made approximately 1 week prior to Visit 2 (unless the randomization visit occurs within 1 week of screening (V1)) and also prior to Visit 5, to remind the subject to complete the bladder diary and to review instructions on proper completion. Bladder diary completion may be verified via remote review of electronic data.

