| 1.2
14 Apr 2014 | PA 5
3 Mar 2014 | Protocol amended to include lighter weight cohort (Cohort 2 - subjects $\leq 25$ kg), originally planned to be studied under a separate protocol (A0221074). | 
 
The SAP has been amended to describe the analyses for Cohort 2. The intention is to analyse and summarize each cohort separately, therefore additional sections have been added into the SAP specifically to describe the Cohort 2 analyses and summaries.
 
   |
| 2.0
25 Feb 2020 | N/A                | Prior to DB Release  | 
 
Removal of figures and listings that have been removed from the List of Tables (LOT) as part of the TLF reduction exercise. The data presented in the figures that have been removed are presented in tables.
 
Exploratory analyses and subgroup figures removed as these won't be included in the CSR. Some have been replaced by descriptive subgroup summary tables instead.
 
As some subjects will only record micturitions in their bladder diary (if they are not catheterizing) and some will only record catheterizations (if they only catheterize), these two endpoints will only be calculated for subjects with <math>>0</math> episodes at baseline.
 
Section 8.2.5 (Other Adverse Event Reporting) has been updated to clarify that the lag period is only applied if a subject discontinues study medication in the Active Comparator/ Efficacy Phase (otherwise, for subjects who continue into the Safety Extension AEs could be counted twice).
 
Other minor updates to ensure SAP is aligned with how results are being presented in tables, figures and listings.
 
 |

The study is ongoing, and unblinded data from the study have been reviewed by an External Data Monitoring Committee; however that review has not influenced any of the changes documented in this amendment.

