## **8.2. Statistical Analyses**

### **8.2.1. Cohort 1: Primary Analysis**

Change from baseline to Week 12 in the primary endpoint will be analysed using an ANCOVA including terms for treatment group, baseline (for the endpoint being analyzed) and baseline weight. The Least Squares mean change from baseline for each treatment group, standard error, 95% confidence intervals and p-values associated with the Least Squares mean changes from baseline will be presented.

All endpoints will also be summarized descriptively for each treatment group, by timepoint as for a continuous endpoint. Should any of the assumptions of the analysis methods not be adequately met, alternative procedures will be used and fully documented.

The following primary comparisons of interest will be assessed:

- Change from Baseline to Week 12 for fesoterodine 4 mg PR.
- Change from Baseline to Week 12 for fesoterodine 8 mg PR.

The Least Squares means and 95% confidence intervals for the difference between each fesoterodine dose group and oxybutynin will also be calculated.

The following secondary comparisons will be assessed using 95% confidence intervals for the difference between treatment means (for the change from baseline to Week 12):

- Fesoterodine 4 mg PR vs Oxybutynin.
- Fesoterodine 8 mg PR vs Oxybutynin.

As these secondary comparisons are based on an estimation approach, no formal statistical hypothesis testing will be performed. Conclusions will be based on point estimates and confidence intervals.

Forest plots presenting the mean and 95% confidence intervals for the change from baseline for Fesoterodine 4mg PR, Fesoterodine 8mg PR and Oxybutynin will be produced. In addition the mean difference and its associated 95% confidence interval between change from baseline for Fesoterodine 4 mg PR vs. Oxybutynin and Fesoterodine 8 mg PR vs. Oxybutynin will be also presented in a separate plot.

The primary analysis will be based on the Full Analysis Set (FAS). The secondary analysis set will be the Per Protocol Analysis Set (PPAS).

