### **8.2.3. Secondary Analyses**

All secondary endpoints will be analysed as for the primary analyses as defined for each respective cohort using the appropriate full analysis set. A further analysis of the key secondary endpoints of Bladder compliance and IDC will use the per protocol analysis set.

The presence of IDC will be analyzed as for discrete endpoints.

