|   | PPAS (Cohort 2) | Week 12    | Categorical summaries   | No imputation               | Secondary analysis (for Cohort 2) |
| Change in bladder compliance at week 12 relative to baseline                        | FAS (Cohort 1)  | Week 12    | ANCOVA – hypothesis testing approach; Descriptive statistics. | BOCF/LOCF (for ANCOVA only) | Secondary analysis (for Cohort 1) |
|   | FAS (Cohort 2)  | Week 12    | ANCOVA – estimation approach; Descriptive statistics.         | BOCF/LOCF (for ANCOVA only) | Secondary analysis (for Cohort 2) |
|   | PPAS (Cohort 1) | Week 12    | ANCOVA – hypothesis testing approach; Descriptive statistics. | No imputation               | Secondary analysis (for Cohort 1) |
|   | PPAS (Cohort 2) | Week 12    | ANCOVA – estimation approach; Descriptive statistics.         | No imputation               | Secondary analysis (for Cohort 2) |
| Change in Bladder volume at first IDC at week 12 relative to baseline               | FAS (Cohort 1)  | Week 12    | ANCOVA – hypothesis testing approach; Descriptive statistics. | BOCF/LOCF (for ANCOVA only) | Secondary analysis (for Cohort 1) |
|   | FAS (Cohort 2)  | Week 12    | ANCOVA – estimation approach; Descriptive statistics.         | BOCF/LOCF (for ANCOVA only) | Secondary analysis (for Cohort 2) |
| Change in mean number of micturitions per 24 hours at Week 12 relative to baseline. | FAS (Cohort 1)  | Week 12    | ANCOVA – hypothesis testing approach; Descriptive statistics. | BOCF/LOCF (for ANCOVA only) | Secondary analysis (for Cohort 1) |
|   | FAS (Cohort 2)  | Week 12    | ANCOVA – estimation approach; Descriptive statistics.         | BOCF/LOCF (for ANCOVA only) | Secondary analysis (for Cohort 2) |
| Change in mean number of incontinence episodes per 24                               | FAS (Cohort 1)  | Week 12    | ANCOVA – hypothesis testing approach; Descriptive statistics. | BOCF/LOCF (for ANCOVA only) | Secondary analysis (for Cohort 1) |

| Endpoint   | Analysis Set   | Assessment | PLANNED Statistical Method                                    | Missing Data                | Interpretation                    |
|--|----------------|------------|---|-----------------------------|-----------------------------------|
| hours at Week 12 relative to the baseline  | FAS (Cohort 2) | Week 12    | ANCOVA – estimation approach; Descriptive statistics.         | BOCF/LOCF (for ANCOVA only) | Secondary analysis (for Cohort 2) |

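### Restricting incontinence and urgency to subjects with episodes at baseline biases the within-arm change towards improvement if some zero-baseline subjects are not truly dry, and leaves new-onset episodes out of the endpoint

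*SAP*

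**What the plan says.** Protocol 2.2.2.1 lists "Mean number of incontinence episodes/24 hrs" with no condition on the baseline value. Urgency is limited only to sensate subjects. SAP 6.1.2 adds to both endpoints: "This endpoint will only be calculated for subjects with >0 episodes at baseline". The same sentence stands under the separate micturition and catheterization counts. For those two the SAP change log (Table 1, version 2.0) gives the reason: "As some subjects will only record micturitions in their bladder diary (if they are not catheterizing) and some will only record catheterizations". Nothing in the SAP explains the rule for incontinence or urgency.

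Entry is urodynamic. Protocol 4.1 asks for neurogenic detrusor overactivity "confirmed urodynamically at Visit 2, by detrusor overactivity or decreased bladder compliance, with decreased maximum cystometric bladder capacity" and sets no minimum number of episodes. The Full Analysis Set (SAP 5.1) has no diary condition.

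The baseline comes from a short diary (Protocol 7.1.2): "A bladder diary will be completed for 3 consecutive days (with a minimum of 2 days".

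On analysis, SAP 8.2.3 says: "All secondary endpoints will be analysed as for the primary analyses as defined for each respective cohort using the appropriate full analysis set". For Cohort 1, SAP 8.2.1 says that "p-values associated with the Least Squares mean changes from baseline will be presented", and SAP 8.2.6 labels both incontinence and urgency "ANCOVA – hypothesis testing approach; Descriptive statistics". Cohort 2 is estimation only (SAP 4.1, 8.2.2).

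**The concern.** For micturitions or catheterizations, a zero can mean that the subject does not empty the bladder that way, so the count does not apply. For incontinence, or for urgency in a sensate subject, zero is a valid observation.

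The diary that decides who is counted is also the baseline value. Subjects whose short diary happened to catch an episode stay in; subjects with the same underlying rate whose diary happened to be dry go out. The included group's baseline is therefore too high on average, and its mean falls at Week 12 without any drug effect. The Cohort 1 p-values compare each arm's change with zero, so no control arm removes this fall. In Cohort 2 the same shift enters the least squares means and confidence intervals.

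A child with a dry baseline diary who has episodes at Week 12 also appears nowhere in these endpoints, including their descriptive summaries. The protocol's development rationale (1.2) names prevention of incontinence, as well as its reduction, as an aim of therapy.

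**Working it through.** **1. Which test the plan uses.** The documents state no figure for incontinence or urgency, so the check starts from the primary endpoint (Protocol 9.1): change 70 mL, SD 120 mL, n = 33 per group, two-sided 5%. A one-sample t-test has noncentrality (70/120) × √33 = 3.35 on 32 degrees of freedom. Power is 90.1%, and 33 is the smallest n that reaches 90%. A two-sample reading gives 65.9%. The plan's test is therefore the within-arm change against zero, and SAP 8.2.3 carries that method over to the secondary endpoints.

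**2. Expected change with no drug effect.** Let Y0 and Y1 be the diary means at baseline and Week 12. If true rates do not change, the all-subject mean change is zero, so

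E[Y1 − Y0 | Y0 > 0] = −E[Y1 | Y0 = 0] × P(Y0 = 0) / P(Y0 > 0).

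This is negative whenever any excluded subject has a non-zero true rate, and zero if all of them are truly dry.

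**3. Size.** Assumptions: true rates follow a gamma distribution with mean m per day and shape k, counts are Poisson, and diaries cover D = 3 days. Then

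- P(Y0 = 0) = (k / (k + Dm))^k
- E[Y1 | Y0 = 0] = mk / (k + Dm)
- mean baseline of included subjects = m / P(Y0 > 0)

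Example, m = 0.5 and k = 1: P(Y0 = 0) = 1/2.5 = 0.40; E[Y1 | Y0 = 0] = 0.5/2.5 = 0.20; shift = −0.20 × 0.40/0.60 = −0.133/day; included baseline = 0.5/0.60 = 0.833; ratio 16%.

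For k = 0.5 to 2, the last two columns come from a simulation of the SAP's ANCOVA with no true change (three arms of 33, baseline and weight as covariates, 3,000 runs per scenario):

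| Mean/day | Zero at baseline | Spurious change/day | % of included baseline | Type I error, >0 only | Type I error, all subjects |
|---|---|---|---|---|---|
| 0.5 | 33-50% | −0.125 to −0.139 | 12-19% | 12-25% | about 6% |
| 1 | 16-38% | −0.076 to −0.087 | 5-6% | 7-10% | 5-7% |
| 2 | 6-28% | −0.033 to −0.059 | about 2% | 6-7% | about 6% |
| 3 | 3-23% | −0.019 to −0.047 | about 1% | 5-6% | about 5% |

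Adjusting for baseline does not remove the shift, because the least squares mean is taken at the selected subjects' own mean baseline.

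**4. Comparison with oxybutynin.** In the same runs, the fesoterodine-oxybutynin difference in the restricted set was falsely significant 4.5-5.4% of the time. Selection uses a pre-randomization value, so the shift is the same in each arm and cancels.

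**5. Effect of including zeros when the drug works.** Take m = 0.5, k = 1 and a true 50% reduction. The included subjects' true rate is 0.833 − 0.133 = 0.70, so their observed change is 0.35 − 0.833 = −0.483/day. Of this, −0.35 is real and −0.133 is regression to the mean. Averaging in the 40% with zero baseline, as if they stayed at zero, gives 0.60 × −0.483 = −0.29. Their Week 12 episodes add 0.40 × 0.10 = 0.04, giving −0.25. Across k = 0.5 to 2 the restricted change is −0.56 to −0.44 against −0.25 for all subjects, which is 43-56% smaller.

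**The case against.** Several stronger readings are tempting, and the documents do not support them.

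- A reader might infer that worsening on treatment cannot appear in the endpoint. It can: any increase in a subject with episodes at baseline counts in full. Only new onset from a zero baseline is missing. New onset could still be reported as an adverse event, since Protocol 8.3 includes worsening of the underlying disease, but that is not an efficacy summary.
- A reader might infer that the comparison with oxybutynin is biased too. It is not (step 4). It does describe only subjects symptomatic at baseline.
- A reader might treat the departure from the protocol as an error in itself. Protocol section 9 lets the SAP modify planned analyses; only major changes to the primary endpoint or its analysis need an amendment. The change log's silence on incontinence and urgency also proves little, because a log lists changes only. What stands is that the SAP gives no reason anywhere.

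The size is not known. The documents give no episode rates, and the model contains no truly dry subjects. If nearly all subjects have frequent episodes, or the excluded ones are dry at both visits, the bias is small or nil. Carrying the baseline forward for missing Week 12 diaries would also dilute it.

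Measuring improvement in subjects who have the symptom is a legitimate aim, because subjects at zero cannot improve. And without a placebo arm, a within-arm change does not isolate a drug effect whether or not zeros are included. Both points stand. Neither justifies testing that subset against zero when the same short diary defines it.

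**Conclusion.** The concern holds, conditionally. If some zero-baseline subjects have a non-zero true rate, the restriction biases the Cohort 1 within-arm test of incontinence and urgency towards improvement and shifts the Cohort 2 means and intervals the same way. It also removes new-onset episodes in zero-baseline subjects from the endpoint.

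Under the assumed gamma-Poisson rates and 3-day diaries, the effect runs from about 1% of the included baseline with near-nominal error (3/day) to 12-19% with type I error of 12-25% (0.5/day). These are secondary endpoints. The primary endpoint, maximum cystometric capacity, is unaffected, and the stated hypothesis (SAP 4.1) concerns that endpoint alone. The change is worth making, but the trial's main conclusion does not depend on it.

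**What to change.** In SAP 6.1.2, 8.2.3 and 8.2.6:

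- Add an analysis of change in incontinence for all Full Analysis Set subjects with a baseline diary, and of change in urgency for all sensate Full Analysis Set subjects with a baseline diary, zeros included. Base any within-arm p-value against zero on this analysis.
- Present the >0 subset alongside it as a descriptive estimate in symptomatic subjects, and state why it is shown.
- Add a table of zero versus >0 episodes at baseline by zero versus >0 at Week 12, by arm, for both endpoints.
- Keep the restriction for the separate micturition and catheterization counts.

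No new data are needed. The direct cost is SAP wording and extra tables. The sponsor should also expect a noticeably smaller mean change, about half if many subjects have zero baselines (step 5). In the worked example, 0.193 of the 0.233/day drop comes from averaging in subjects who cannot improve, and 0.04 from their Week 12 episodes. The larger restricted figure was itself partly regression to the mean, so not all of the difference is lost drug effect.

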### Diary Data

For the analysis involving diaries, time-points will be defined as non-overlapping periods. See [Appendix B](#) for definition of time intervals. Missing daily micturition data will be estimated as the following:

1. If one out of three days is missing, the mean of the remaining days will be used to impute the micturition data for the missing day/days.
2. The LOCF/BOCF imputations will be carried out for time-intervals with missing diary data. For intervals where less than two days of diary data are available, the previous available 3-day post-baseline interval values will then be carried forward.

Micturition volume is collected on one day only therefore if it is missing at a visit the previous visit's data will be carried forward.

Note: In subjects who withdraw after a minimum of 2 weeks of treatment, attempts should be made to perform a urodynamic assessment, provided that they have not missed any doses in the three days previous to the visit.

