- g. Urinalysis: Urine microscopy, culture, and sensitivity to be performed in the event of the presence of symptoms (eg, fever, flank pain), positive leucocytes and/or nitrites on urinalysis, or if the subject has a documented history of vesicoureteral reflux (VUR).
- h. Serum pregnancy test at Visit 1, urine pregnancy test at all other visits. Only for female subjects of child-bearing potential. Pregnancy tests may also be repeated as per request of IRB/IECs or if required by local regulations.
- i. PK blood sampling only in subjects randomized to treatment with fesoterodine during the active comparator/efficacy phase. A maximum of three PK samples will be collected from each subject. Subjects randomized to treatment with oxybutynin will not be required to provide PK samples. In the event of subject withdrawing early from the active comparator phase prior to Visit 3, PK samples should be obtained at the early termination visit.
- j. At Visit 3 PG samples only in subjects randomized to treatment with fesoterodine during the active comparator phase, and who do not have prior laboratory documentation of their CYP2D6 genotype. At Visit 5 (or early withdrawal from the active comparator/efficacy phase), only subjects who were on oxybutynin who will continue into the safety extension phase and who do not have prior laboratory documentation of their CYP2D6 genotype.
- k. Urodynamic studies: subjects who demonstrate a clinically relevant increased detrusor pressure or other urodynamic findings suggestive of worsening condition compared to baseline should not be allowed to continue into the safety extension phase. Consideration should be given to imaging of upper urinary tract (for example, videourodynamics, or ultrasound) according to accepted local standard of care in subjects with VUR, or other conditions that predispose to upper urinary tract dysfunction or damage.
- l. Bladder diary and dosing log data will be recorded on the same electronic data capture device. The bladder diary will be completed for 3 days prior to Visits 2 and 5; the dosing log will be completed on a daily basis. Subjects and/or their caregivers should be re-educated and re-trained if review of data suggests that the bladder diary or dosing log are not being completed correctly.
- m. Electronic data capture device should be collected at Visit 2 for subjects who are not randomized, or at other visits if the subject discontinues.

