**10.2. Appendix B: DEFINITION OF ASSESSMENT WINDOWS**

There will be no visit windows defined for this study. The target observation will be that taken at a time closest to when the scheduled visit should have occurred.

The LOCF1 rule will be used to impute data at missing visits (ie, the last non-missing reading prior to the window will be used; the observation does not have to have fallen inside a window).

Diary data should be completed within +/- 14 days of a visit whether this is a formal visit or a withdrawal visit.

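### Two SAP diary derivations are wrong as written (part-days counted as full days; combined volume divided by micturitions only), and Appendix B's ±14-day diary tolerance conflicts with the pre-visit diary schedule

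*SAP*

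**What the plan says.** **Diary days.** SAP 6.1.2 defines each per-24-hours endpoint as a total count divided by the number of diary days. A note under catheterizations defines a diary day as any calendar day with diary completion, whether or not it covers 24 hours, and gives an example: "if a diary has been completed for 3 complete days and the morning of the fourth day, this would count as 4 days". The note extends this to all the per-24-hours endpoints: micturitions, catheterizations, the two combined, incontinence and urgency.

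**Combined volume.** The last endpoint in the section covers micturitions or catheterizations together, but its definition reads: "The mean voided volume per micturition or catheterization will be calculated as sum of voided volume divided by the total number of micturition episodes", restricted to episodes with a recorded volume above zero. The SAP expects subjects with no micturitions at all. The version 2.0 row of its change table notes that "some will only record catheterizations (if they only catheterize".

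**Diary timing.** Appendix B says no visit windows are defined and then sets this tolerance: "Diary data should be completed within +/- 14 days of a visit whether this is a formal visit or a withdrawal visit". Footnote l to the SAP schedule says "The bladder diary will be completed for 3 days prior to Visits 2 and 5". Protocol 7.1.2 asks for the diary "for 3 consecutive days (with a minimum of 2 days) during the week prior to Visit 2 (baseline) and Visit 5 (Week 12".

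**Analysis route.** SAP 8.2.3 states: "All secondary endpoints will be analysed as for the primary analyses as defined for each respective cohort using the appropriate full analysis set".

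**The concern.** A rate per 24 hours needs a denominator in units of 24 hours. Counting a morning as a day adds a full unit to the denominator and only a fraction of a day's events to the numerator, so the rate is biased downward. In Cohort 1 the comparison of interest is change from baseline within each arm, and SAP 8.2.6 gives micturitions, incontinence and urgency a hypothesis-testing analysis. If part-days are more frequent at one visit than the other, the test of within-arm change picks up the artefact, and no between-arm contrast removes it.

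The combined-volume definition does not match its title: the title covers two kinds of event and the denominator counts one.

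The ±14-day tolerance carries no pre-dose limit. The first dose is given at Visit 2 (Protocol 6.2), so as written a diary kept on treatment could serve as baseline. Oxybutynin subjects who continue are moved to fesoterodine from Visit 5 (Protocol 5.2), so a late Week 12 diary in that arm could reflect washout or the other drug.

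**Working it through.** **1. Part-day as a full day**

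Input from SAP 6.1.2: three complete days plus one morning. The SAP's count is reproduced as 3 + 1 = 4 days.

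Assumed: *f*, the share of a day's events that falls in the morning, from 0.25 to 0.5.

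Reported rate / true rate = (3 + *f*)/4.

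- *f* = 0.5: 3.5/4 = 0.875, so 12.5% too low.
- *f* = 0.25: 3.25/4 = 0.8125, so 18.75% too low.

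Write *b* for this shortfall (0.125 to 0.1875). Consequences for change from baseline:

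- *Part-day at both visits.* Every change is multiplied by 1 − *b*. A true change of −1.0 per 24 h is reported as −0.875 to −0.8125.
- *Part-day at one visit, no true change.* At an assumed constant 4 episodes per 24 h, the false change is 4 × 0.125 = 0.50 to 4 × 0.1875 = 0.75. It is a false decrease if the part-day is at Week 12, and a false increase if it is at baseline.
- *Arm mean.* If the proportion of subjects with a part-day differs between visits by Δp, the mean change at that rate shifts by 4 × *b* × Δp. For Δp = 0.10 this is 0.05 to 0.075. If the proportions are equal, no false mean change arises: true change is attenuated in proportion, and subjects with a part-day at only one visit add noise.

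The missing-data rule does not repair this. SAP section 7 imputes a missing day from the mean of the remaining days, and then says: "For intervals where less than two days of diary data are available, the previous available 3-day post-baseline interval values will then be carried forward". A part-day has been counted as a collected day, so neither rule is triggered.

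**2. Combined volume**

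Let Vm and Vc be the total micturition and catheter volumes, and Nm and Nc the numbers of episodes with volume above zero.

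- Endpoint as named: (Vm + Vc)/(Nm + Nc).
- SAP formula, if the sum includes catheter volume: (Vm + Vc)/Nm.
- Ratio: (Nm + Nc)/Nm = 1 + Nc/Nm, whatever the volumes.

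Illustration with assumed volumes of 100 mL per void and 150 mL per catheterization:

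| Nm | Nc | SAP formula (mL) | As named (mL) | Ratio |
|---|---|---|---|---|
| 6 | 0 | 100 | 100 | 1.0 |
| 4 | 2 | 175 | 116.7 | 1.5 |
| 3 | 3 | 250 | 125 | 2.0 |
| 2 | 4 | 400 | 133.3 | 3.0 |
| 0 | 6 | undefined | 150 | – |

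If the sum of voided volume excludes catheter volume, the formula becomes Vm/Nm, which is the micturition-only endpoint already defined earlier in the section. On either reading Nm = 0 gives division by zero.

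**3. Diary timing**

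| Source | Diary days accepted, relative to the visit |
|---|---|
| Protocol 7.1.2 | within the 7 days before |
| SAP Appendix A, footnote l | 3 days, before |
| SAP Appendix B | −14 to +14, that is 29 days, 14 of them after the visit |

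Protocol 6.2 and 6.7 have the diary reviewed at Visits 2 and 5, which presupposes that it is already complete. SAP section 7 refers to Appendix B for non-overlapping diary intervals, but Appendix B defines none.

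**The case against.** **The part-day rule is an open convention.** It is stated with an example and applied alike to all arms and both visits. Diaries made only of complete days, which is what the protocol asks for, are unaffected. Part-day frequency is unknown, so every study-level figure is hypothetical, and the arm-level shift of 0.05 to 0.075 is small. All of this stands. It limits the size of the problem but does not turn the quotient into a 24-hour rate.

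**Removing part-days has its own cost.** A Week 12 diary that falls below two days becomes baseline carried forward, with zero change. That discards the subject's observed change to cure a partial understatement. This is a fair point and bears on which fix to prefer.

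**The combined volume is probably a drafting slip.** SAP section 7 uses micturition volume where Protocol 7.1.2 speaks of both kinds of event, so the word may be shorthand for both. The SAP also defines volume per catheterization separately, so catheter-only subjects do have a volume endpoint, and the combined volume has no row in the SAP 8.2.6 table. These points soften the consequence. But SAP 6.1.2 elsewhere keeps the two terms apart, and SAP 8.2.3 sends all secondary endpoints to analysis, so the literal formula still needs correcting.

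**The ±14 days may be an outer tolerance.** It may be meant for withdrawal visits, for which no pre-visit week can be planned. Reminders (Protocol 6.11) and diary review at the visits make a post-dose baseline diary unlikely. Appendix B also targets the observation closest to the scheduled time. It still sets no pre-dose limit, and the passages disagree.

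**Conclusion.** The concern holds on all three parts. It should be fixed, but it does not threaten the trial's main result: maximum cystometric capacity, its analysis and the sample size are untouched.

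- *Part-days:* the rate is 12.5% to 19% too low in the SAP's own example, given the assumed morning share. True changes shrink by the same fraction when both visits have such a part-day. A false mean change needs an imbalance in part-day frequency between visits, about which the documents say nothing.
- *Combined volume:* inflated by exactly 1 + Nc/Nm if catheter volume is summed, redundant if it is not, and undefined for catheter-only subjects either way.
- *Timing:* a conflict between passages that matters only for off-schedule diaries. The post-switch problem is confined to the Cohort 1 oxybutynin arm.

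Confidence in the reading of the text is high. The effect on the reported results cannot be sized from the documents.

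**What to change.** 1. Count only complete 24-hour periods and the episodes within them, or divide by recorded hours/24. The second option keeps the part-day data and avoids pushing diaries below the two-day minimum, but it needs diary start and stop times, which Protocol 7.1.2 does not list among the recorded items.
2. For the combined volume, make numerator and denominator both cover all micturitions and catheterizations with a recorded volume above zero.
3. Reconcile Appendix B with Protocol 7.1.2 and footnote l, so that baseline diary days precede the first dose and Week 12 diary days fall on or before Visit 5 or the last dose of randomised treatment.

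The cost is SAP wording and derivation code. Under complete-period counting or the tighter timing rule, some diaries may be lost. Diaries are scheduled only at Visits 2 and 5, so a subject whose Week 12 diary is excluded would be analysed with zero change. A subject left without a valid baseline diary has nothing to carry forward and drops out of that endpoint. The documents do not show how many subjects this would affect.
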